2.3. Secondary objectives

- To determine the impact of the type of attire worn by adolescents on in-store communication between sellers and customers, specifically in terms of dissuading use.
- To discern the differences in regulation compliance-related behaviors between e-cigarette and cigarette retailers.

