5.2. Treatment procedures

Before entering a store, the simulated buyers will observe and record the location and

exterior advertising from a hidden corner.

After that, the simulated buyers will enter the store and attempt to buy e-cigarette products. If the seller asks about their age, they will tell the seller that they are adults (18 years old or above) but will not show their ID cards or give any proofs to mimic the real-world situation. If the seller asks about buyer's smoking status, the buyer will claim that he/she has never tried any tobacco products including both e-cigarettes and cigarettes, and wants to buy e-cigarettes out of curiosity because his/her friends are using these products. The buyer will ultimately attempt to buy the cheapest e-cigarette product in the store for the budget reason, but he or she will not reveal this before asking about the price. To reduce potential biases caused by adolescent buyers' personalities and communication skills, a soft script will be developed to standardize the in-store interactions as much as possible (see Appendix 2).

After the assessment (approximately 10-15 minutes), simulated buyers will immediately leave the store and complete the rest of data entry to optimize retention. They will note the seller's responses during the visit, including whether or not inquiring about age, checking ID card, dissuading uses, and ultimately selling products. In addition, they will document the seller's demographic characteristics, marketing messages, interior decorations and signs. The detailed information about outcome measures is shown in Section 6. Data will be inputted via a self-developed instrument embedded in the online survey platform called Questionnaire Star accessed by smart phones.

After leaving the e-cigarette store, simulated buyers will search for the nearest cigarette shop and conduct a similar visit intervention. They will firstly observe the store's location and exterior advertising. Then, they will enter the shop and attempt to purchase a pack of cigarettes. If cigarette seller asks, they will answer that they are adults now and have never smoked. The adolescents will similarly record the behaviors and claims of the sellers in cigarette stores. The detailed information about outcome measures is shown in Section 6.

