8.3. Analysis of secondary outcomes

Secondary outcomes, including inquiring about the buyer's age, requesting ID cards for age verification, and dissuading buyers from use, will be analyzed in a similar manner to the primary outcome. Chi-square tests will be used to detect the statistical significance of differences between the two study groups, and logistic regression models, adjusted for covariates and appropriate for the distribution of the outcomes, will be employed. Additionally, similar national maps describing geographic variations will be generated.

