Appendix 2 Communication script in the e-cigarette store

Soft script

When the simulated buyer, acting as a customer, communicates face-to-face with the seller in an e-cigarette store, the main information recorded includes: successful purchases of e-cigarette products, inquiries about age, requests to show ID cards, dissuasion from using e-cigarettes, price information, and marketing strategies (such as the store clerk adding you on WeChat). You can use the following conversational sentences to naturally gather the above information:

Other key points: advertising area, warning slogans, decorations, product types, flavor recommendations, information conveyed, and discounted prices.

Legal requirements: (record only)

- **Does the seller in the e-cigarette store ask about your age?**
- **Have you been asked by the seller to show your ID card?**

1. When you walk into the store or approach the counter, first glance at the wall to see if there is a tobacco license. Then look at the e-cigarette products, paying attention to any "No use by minors" warning signs and "Smoking or vaping is harmful to health" warning signs. Continue to pretend you are browsing the store.
2. Typically, the seller will notice you immediately and ask what you are looking for. You should respond with "I'm just browsing," "I'm here to learn about the products," or "My friend uses e-cigarettes, and I'm here to check them out."
3. The seller will likely ask if you have used e-cigarettes or smoked before. You should respond, "I have never used them before." At this point, some sellers may advise you not to buy or try them.

4. You should ask the seller, "Do you have any recommendations?" The seller will likely recommend a lighter flavor product and hand it to you. You then ask, "Is this detachable?" or "Can this be used continuously?" to determine the type of e-cigarettes sold in the store. While doing this, take the opportunity to look around to see if there are disposable e-cigarettes and open-system e-cigarettes, as well as whether protective cases and lanyards are sold at the counter.

5. During the ongoing product viewing phase, point to the various e-cigarette cartridges on the counter or shelf and ask the seller about their differences. Then further inquire, "Which ones sell well?" or "What do people often buy?" or "Which are popular?" Take note of the first and second flavors mentioned by the clerk. If the seller offers you a sample, be sure to refuse!

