No, the e-cigarette store is not open (please skip to the end of the questionnaire and submit your answer sheet)

No, the seller is not in the store (please skip to the end of the questionnaire and submit your answer)

No, other _____ * (please skip to the end of the questionnaire and submit your answer sheet)

15. Is the tobacco retail license visible [Single choice question] *

Yes

No

16. Is there a "No use by minors" slogan in the store (excluding slogans on product packaging) [Single-choice question] *

Yes

No

17. Are there any of the following health warning signs in the store (excluding slogans on product packaging) [Single choice question] *

Yes, there is a "Smoking is harmful to health" sign

Yes, there is a "E-cigarettes are harmful to health" sign

Yes, both of the above exist

No

18. Are there children's toys, car models, figurines, and/or other decorations placed on the shelves or counters? [Note that these decorations need to be targeted at teenagers.] [Single Choice Question] *

Yes, specifically _____ *

No

19. Gender of the seller: (When there are multiple sellers, this question refers to the seller who communicates with the simulated buyer the most. The same applies to the questions below.)

Male

Female

20. Age of the seller (the simulated buyer needs to estimate) [Single-choice question] *

18-24 years old

25-29 years old

30-39 years old

>40 years old

21. Did the seller ask the simulated buyer if he or she was an adult? [Single Choice Question] * -----Questions such as "Are you an adult?" "Are you over 18?" "How old are you?" "Are you a student?" etc.

Yes

No

22. Did the seller ask to see the simulated buyer's ID? (If the seller requires you to fill in identity information on the system, please select Yes.) [Single Choice Question] *

Yes

No

23. Did the seller ask the simulated buyer to leave? (No sales communication) [Single Choice Question] * ----- If the seller does not check the age until the simulated buyer pays, the sales communication has been completed at this point. In this case, you should select "No" and continue to fill in the questionnaire.

○No

- Yes, the seller asked you (the simulated buyer) to leave without asking about their age. (Please skip to the end of the questionnaire and submit your answer.)
- Yes, the seller asked you (the simulated buyer) to leave after asking their age. (Please skip to the end of the questionnaire and submit your answer.)

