- Yes, the seller asked you (the simulated buyer) to leave after knowing that he or she did not have an ID card. (Please skip to the end of the questionnaire and submit your answer.)

In-store communication and records 2

24. Does the e-cigarette store sell the following types of e-cigarettes and accessories
[Multiple choice questions] **

Disposable e-cigarettes ----- Disposable e-cigarettes refer to those e-cigarettes that cannot be disassembled, refilled, or changed by the user and are thrown away after use. They can also be rechargeable. For example, the seller might describe them to you as "rechargeable for 1,000 puffs."

Reloadable e-cigarettes and/or cartridges ----- Reloadable e-cigarettes usually consist of two parts: a cigarette rod and a cigarette cartridge. The cigarette rod can be recharged and reused, while the cigarette cartridge is thrown away after use.

Open e-cigarettes that the user refills with e-liquid himself or herself ----- The e-liquid tank of open e-cigarettes is open and refillable. It can be refilled 3-6 times for continued use. The atomizer has a long service life.

Auxiliary accessories for e-cigarettes, such as protective cases, lanyards, etc.

Other, _____

25. Other items sold in the e-cigarette stores: [Multiple choice questions] *

No products other than e-cigarettes are sold

Power bank rentals

Addictive substances, such as tobacco, alcohol, and betel nut

Other _____

26. Did the seller proactively dissuade the simulated buyer from trying e-cigarettes? [Single Choice Question] * ----- The seller will tell you (the simulated buyer) that e-cigarettes are harmful, addictive, impossible to quit, don't try them, etc., in an attempt to discourage you from buying them.

Yes

No

27. The most popular flavor recommended to you (the simulated buyer) by the seller is [fill in the blank] * ----- Ask the seller, "With so many varieties, what are the differences?" and then, "Which one sells better?"

28. The second most popular flavor recommended to you (the simulated buyer) by the seller is [fill in the blank] * ----- If the seller only recommended one flavor in the previous question, you can fill in "none" for this question.

29. Is there a "Free Trial" sign or disposable filters in the store [Single-choice question] * -----Pay attention to whether there are disposable filters at the cashier]

Yes

No

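### Appendix 4 ends the form at Question 23 for every buyer asked to leave, so dissuasion (Question 26), a secondary outcome, is blank by design for those stores and has no coding rule

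*Protocol*

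**What the plan says.** Dissuasion is one of three secondary outcomes (Protocol 6.2, SAP 2.2.1). It is also the subject of a secondary objective on in-store communication, "specifically in terms of dissuading use" (Protocol 2.3). Protocol 5.2 has buyers note the seller's responses, "including whether or not inquiring about age, checking ID card, dissuading uses, and ultimately selling products". For analysis, Protocol 8.3 lists it among the outcomes to be tested by chi-square and adjusted logistic regression: "dissuading buyers from use, will be analyzed in a similar manner to the primary outcome". SAP 2.3.3 says the same.

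The form in Appendix 4 is routed as follows. Question 23 asks whether the seller told the buyer to leave, and labels this as no sales communication. It has three 'Yes' options: asked "to leave without asking about their age. (Please skip to the end of the questionnaire and submit your answer"; asked to leave after an age question, with the same instruction to end the form; and asked "to leave after knowing that he or she did not have an ID card. (Please skip to the end of the questionnaire". The dissuasion item is Question 26: "Did the seller proactively dissuade the simulated buyer from trying e-cigarettes".

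A note to Question 23 limits who is affected: "If the seller does not check the age until the simulated buyer pays, the sales communication has been completed at this point". Such a visit is answered 'No' and continues.

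Protocol 8.7 foresees buyers being asked to leave. Its statements about the resulting gaps concern the store's internal environment, and its available-data rule covers only in-store environmental characteristics.

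**The concern.** A store whose seller warns the buyer and also sends the buyer away cannot have the warning recorded. The script places possible warnings early, when the seller asks about past use: "At this point, some sellers may advise you not to buy or try them". Two of the three exit options describe an exchange about age or ID before the buyer was sent away, and a seller could also tell a buyer not to try the product while turning the buyer out.

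The trial's hypothesis is that uniforms increase compliant responses, so being asked to leave may be more common in the uniform arm. The blanks would then be related to treatment. Leaving these stores out compares subsets formed after randomisation. Counting them as 'No' removes any warning that accompanied the ejection, and removes more from the arm with more ejections. With neither choice written down, and a statistician who is not blinded (Protocol 7.1.4, SAP 1.1.3), the choice could be made after the results are known.

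**Working it through.** The plan gives no figure on this point to reproduce. The check is a trace of the form, followed by an illustration under assumed rates.

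**1. What a 'Yes' at Question 23 leaves recorded**

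| Outcome | Item | Available when Question 23 = Yes? |
|---|---|---|
| Age inquiry | Question 21 | Yes, asked before the exit |
| ID request | Question 22 | Yes, asked before the exit |
| Dissuasion | Question 26 | No, skipped; no other item records it |
| Purchase (primary) | Question 37 | Skipped, but no sale follows from the answer |
| Free-text remarks | Question 41 | No, skipped, so no fallback |

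**2. Bias in the arm difference**

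The documents give no ejection or dissuasion rates, so every rate here is an assumption. Let T be true dissuasion over all visited stores (30% uniform, 20% casual, a difference of +10 points), L the share with Question 23 = Yes, and r the share of ejecting sellers who also dissuade.

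- Blanks dropped: estimated rate = (T − L·r)/(1 − L)
- Blanks coded 'No': estimated rate = T − L·r
- Bias = estimated difference − 10 points

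| L uniform / casual | r | Dropped | Bias | Coded 'No' | Bias |
|---|---|---|---|---|---|
| 5% / 2% | 0 | 31.58 − 20.41 = 11.17 | +1.2 | 30.0 − 20.0 = 10.0 | 0 |
| | T | 30.0 − 20.0 = 10.0 | 0 | 28.5 − 19.6 = 8.9 | −1.1 |
| | 0.6 | 28.42 − 19.18 = 9.24 | −0.8 | 27.0 − 18.8 = 8.2 | −1.8 |
| 10% / 4% | 0 | 33.33 − 20.83 = 12.50 | +2.5 | 30.0 − 20.0 = 10.0 | 0 |
| | T | 30.0 − 20.0 = 10.0 | 0 | 27.0 − 19.2 = 7.8 | −2.2 |
| | 0.6 | 26.67 − 18.33 = 8.33 | −1.7 | 24.0 − 17.6 = 6.4 | −3.6 |
| 20% / 5% (stress) | 0 | 37.50 − 21.05 = 16.45 | +6.4 | 30.0 − 20.0 = 10.0 | 0 |
| | T | 30.0 − 20.0 = 10.0 | 0 | 24.0 − 19.0 = 5.0 | −5.0 |
| | 0.6 | 22.50 − 17.89 = 4.61 | −5.4 | 18.0 − 17.0 = 1.0 | −9.0 |

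Dropping is unbiased if ejecting sellers dissuade at their arm's overall rate. Coding 'No' is unbiased if they never do. No scenario reverses the sign.

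**3. Scale**

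With 1,080/2 = 540 stores per arm, the 95% half-width is 1.96·√(DE·(0.3·0.7 + 0.2·0.8)/540). With DE = 1 this is 5.1 points. With the plan's cluster size 4 and correlation 0.5, DE = 1 + 3·0.5 = 2.5, and it is 8.1 points.

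**4. Which codings bound the answer**

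Suppose stores that complete the form show 30% dissuasion in both arms. An arm's rate is 0.30·(1 − L) with blanks 'No', and 0.30·(1 − L) + L with blanks 'Yes'. Uniform minus casual, in points:

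| L | All 'No' | All 'Yes' | Span | Opposite-arm extremes | Span |
|---|---|---|---|---|---|
| 5% / 2% | −0.9 | +2.1 | 3 | −2.9 to +4.1 | 7 |
| 10% / 4% | −1.8 | +4.2 | 6 | −5.8 to +8.2 | 14 |
| 20% / 5% | −4.5 | +10.5 | 15 | −9.5 to +15.5 | 25 |

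Applying the same coding to both arms spans only L uniform − L casual. The worst-case range is L uniform + L casual, and it needs opposite codings.

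**The case against.** The strongest reply is that the skip follows from the form's own definition. Question 23 is labelled as no sales communication. Script step 3, where warnings are expected, is already a conversation about products, so a visit that got that far arguably belongs under 'No' and reaches Question 26. A coding might also be inferred: purchase is likewise skipped and is naturally read as 'No', and dissuasion is to be handled like the primary outcome.

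Part of this stands. The label makes overlap between warning and ejection uncertain and probably limited, and it favours 'No' as the main coding. But the rule is written nowhere, and sales communication is not defined for a visit in which the seller warns and then ejects. No purchase follows from ejection; no warning does not.

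A reader might also infer from the 'no chance' wording in Protocol 8.7 that the plan denies any missing data. That overreads it. The wording concerns overlooked items, and the next sentence foresees ejection and relies on the pilot to show which questions can be completed. What 8.7 lacks is a rule for dissuasion. Protocol 6.2 says this outcome was added after the pilot, so the documents do not show that the pilot check covered it.

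**Conclusion.** The routing gap is certain from the form: dissuasion is unrecorded for every store with Question 23 = Yes, and neither document says how those stores are analysed. Its numerical importance is unknown. It is probably small if ejection is uncommon, or if visits without sales communication rarely contain a warning. In the two more moderate scenarios the largest bias is 3.6 points, below either half-width. It becomes material only if ejection is frequent and unequal between arms. The 9.0-point figure needs 20% versus 5% ejection with 60% of ejecting sellers also dissuading, and is a stress case.

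Two stronger readings should be resisted. Because Question 37 is skipped too, a reader might infer that the primary outcome is compromised; it is not, since a buyer sent away without sales communication made no purchase. A reader might also infer that dissuasion is lost for all refusals; refusals at payment, and warnings without a request to leave, are answered 'No' and reach Question 26.

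**What to change.** If the form can still be changed, move the dissuasion item ahead of Question 23, or repeat it on each of the three exit branches, and analyse it over all visited stores. The cost is one online item, with no extra visits.

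If data are already collected, state in the SAP before database lock that the denominator for dissuasion is all visited stores, with Question 23 = Yes coded 'No' in the main analysis. Add a sensitivity analysis that includes the opposite-arm extremes: blanks 'Yes' in the uniform arm and 'No' in the casual arm, then the reverse. All-'No' and all-'Yes' may be shown beside them but do not give the worst-case bound. The cost is a few sentences and one table. This branch may be the live one, because the Protocol's reference list carries an access date in April 2024, after the planned fieldwork.

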Appendix 5 Telephone protocol

For training the personnel making phone calls, you are attempting to gather information about e-cigarette stores over the phone. You can pretend to be a buyer looking to purchase e-cigarettes. Once you have collected all the information about the e-cigarette stores on the list, please make sure to keep all of it.

Soft Script: Speak cautiously, pretending that you are a buyer attempting to purchase e-cigarettes in the store. You would like to get more information about the e-cigarette stores, such as location, address, and opening hours. Do not ask questions proactively to avoid raising the seller's suspicions. Mention other issues as little as possible to minimize mistakes.

Once the call connects, ask: "**Hello, is your shop still open? I want to buy some e-cigarettes.**" If they answer it's closed, lament: "**Ah, why is it closed... where can I buy some now...**" Pay attention to whether they voluntarily mention:

- Having changed their type of business;
- Providing other contact methods (adding their WeChat, a mobile instant messaging software, or recommending another merchant's phone number);
- Offering online sales (rapid delivery, courier);
- Mentioning illegal flavored e-cigarettes (milk tea cup, bear cup, planet cup, etc.).

If the seller answers the store is closed, you can respond with, "Never mind, I'll look elsewhere."

—> Hang up the call to end it.

Answer the call	Under normal business	Change business	Provide additional contact information	Selling online	Selling illegal flavors	Key information records
1	0	1	1	1	1	“Branded products are not selling well, but

						
milk tea cups have many flavors.” “Add me on WeChat and I will send them to you by local courier.”

1	0	0	0	1	0	
“The store is closed, but if you need it, add me on WeChat and I will contact my friends to sell it to you.”

(1) For the e-cigarette stores that are open —>

You said: "Okay, then I'll come over and see if I have time. Are you at [xxxxx] (check address)?"

—> Hang up to end the call.

(2) Record if no one answers your call:

After dialing, wait until the voice prompt says "Sorry, the number you dialed is temporarily unavailable." This is considered unavailable, and you should mark 0 in Excel.

—> Try to call again after 15 minutes.

—> If the call is connected, follow the soft script above for communication. If still not connected, hang up to end the call.

(3) Record shutdown:

—> If the call is connected, follow the soft script above for communication. If the phone is turned off or disconnected, hang up to end the call.

Note:

Stop calling once you have a list of 40 e-cigarette stores open in each metropolitan area. Submit the list of 40 e-cigarette stores to your supervisors.

For various problems and situations encountered, if the issue is special or difficult to resolve, you can contact your supervisors at any time. Do not force the task to be completed.

Appendix 6 Recruitment poster for simulated buyers

The China Center for Health Development Studies at Peking University will conduct a survey on the behaviors and marketing strategies of e-cigarette retail stores in several major metropolitan areas in China. The survey is expected to begin from July 22-25 and last for about three weeks. Offline training will be provided before the official start date. Scan the QR code to sign up, and you will gain valuable research experience and generous compensation. This is also a great opportunity to visit various places in China and explore local delicacies.

Recruitment Criteria:

University students aged 18 or 19 currently studying in Beijing.

Have never used cigarettes or e-cigarettes.

Possess good communication skills and a sense of responsibility, and can commit to the training and the entire survey period.

Benefits:

Accommodation and transportation fees covered, with a daily compensation of CNY 350.

Outstanding researchers have a chance to receive a surprise gift pack!

After the survey, the research team will verify the quality of the questionnaires and issue a certificate of practice.

QR Code for Registration:

We sincerely look forward to your participation! If you have any questions, feel free to contact us via phone or WeChat: [name].

>>>>>>>>> 暑期调研员
招募

JOIN US

加入
我们

扫码报名，

收获宝贵的科研实践经历+丰厚报酬，
一次游览祖国多地、探索特色美食的绝佳机会！

北京大学中国卫生发展研究中心将对我国多个重
要城市电子烟零售店的环境及营销策略进行调查，
预计7月22-25日开始，为期约3周，将于正式开始
前2日进行线下培训。

● 招募条件

1. 北京在校的18、19岁大学生；
2. 从未使用过香烟和电子烟；
3. 具备良好沟通能力和责任心，能全程参与培训及调研。

● 福利

1. 包住宿和交通费，劳务费每天350元及以上。
优秀调研员有机会获得**惊喜大礼包**哦！
2. 调研结束后，课题组将核实问卷质量后开具实践证明。

真诚期待您的参与！如有疑问，欢迎电话或微信咨询：

[name]

